5 SECONDARY ANALYSIS

5.1 SECONDARY OUTCOMES

1) 'Living at home' at 12 months

The 'living at home' at 12 months outcome will be analysed separately from the 6 months analysis (since the main analysis shall be carried out after 6 months but before the 12 months follow-up data has been collected) and will not be reported in the main report, instead it will be reported in a separate statistical analysis report. The data will be analysed using a generalised linear mixed models as described in section 4.1, with 'living at home' at 12 months as the outcome. The intervention effect with 95% confidence interval and p-value will be reported.

2) Presence of delirium at 3 days, 5 days, and 1 month (CAM)

Presence of delirium is assessed at baseline, 3 days, 5 days, and at 1 month, by the Confusion Assessment Method (CAM) and is a binary variable. A generalised linear mixed model will be used similar to the primary analysis (section 4.1) with presence of delirium at 3 days and 5 days, and

presence of delirium at 1 month as the dependent variable. The model will include intervention arm, baseline CAM, stratification factors (gender and known cognitive decline (IQCODE)) as fixed effects; and centre as a random effect. The model will also include a random interception for each patient. The model will include an interaction between time and randomised group as a fixed effect. The adjusted relative risk between randomised groups with 95% CI and p-value for presence of delirium at 3 days, 5 days, and at 1 month will be estimated from the model.

3) Mortality at 6 months and 12 months

Mortality is measured at 3 days, 5 days, 1 month, 6 months, and 12 month follow-up (*deathyn*) and is a binary variable (0 = dead, 1 = alive). The mortality outcome will be summarised at each time point but will only be analysed at 6 and 12 months. The mortality at 12 months outcome will be analysed separately from the 6 months analysis and will not be reported in the main report, instead it will be reported in a separate statistical analysis report. Mortality at 6 months will be reported in the main statistical analysis report. A generalised linear mixed model will be fitted to the data similar to the primary analysis (see section 4.1) with mortality as the dependent variable. The model will include intervention arm, stratification factors (gender and known cognitive decline (IQCODE)) as fixed effects; and centre as a random effect. The adjusted relative risk and 95% CI and p-value for mortality at each time point will be estimated from the model. Mortality at 12 months will be analysed similar to the 6 months mortality data.

4) New long-term residential care at 1 month and 6 months

New long-term residential care is measured at 1 month and 6 months follow-up (*admitryn*) is a binary variable (0 = No, 1 = Yes). A generalised linear mixed model will be fitted to the data with new long-term residential care at 1 and 6 months as the dependent variable. The model will include intervention arm, gender, and known cognitive decline (IQCODE) as fixed effects, and centre as a random effect. The model will include a random intercept for each patient. The model will include an interaction between time and randomised group as a fixed effect. The adjusted relative risk with 95% CI and p-values for new long-term residential care at 1 month and 6 months will be estimated from the model.

5) Cognitive impairment at 6 months (MoCA)

Cognitive impairment measured at baseline and 6 months by the Montreal Cognitive Assessment (MoCA). This is converted into a binary variable (see section 2.1.2). A generalised linear mixed model will be fitted to the data with cognitive impairment at 6 months as the dependent variable. The model will include intervention arm, baseline MoCA score, gender, and known cognitive decline (IQCODE) as fixed effects; and centre as a random effect. The adjusted relative risk with 95% confidence intervals and p-value for cognitive impairment at 6 months will be estimated from the model.

6) Activities of daily living at 6 months (Barthel index)

Activities of daily living is measured at baseline and 6 months by the Barthel index and is a continuous variable. A linear mixed effects model will be fitted to the data with activities of daily living at 6 months as the dependent variable. The model will include intervention arm, baseline Barthel index score, gender, and know cognitive decline (IQCODE) as fixed effects, as well as centre as a random effect. The intervention effect with 95% confidence intervals and p value for activities of daily living at 6 months will be estimated from the model.

7) Readmission or transfer to hospital at 1 month and 6 months

Readmission or transfer at 1 month and 6 months (*hadmityn*) is a binary variable (0 = No, 1 = Yes). A generalised linear mixed model will be fitted to the data with readmission or transfer to hospital at 1

and 6 months as the dependent variable. The model will include intervention arm, gender, and known cognitive decline as fixed effects, and centre as a random effect. The model will also include a random intercept for each patient. The adjusted relative risk with 95% CI and p-values for activities of daily living at 1 month and 6 months will be estimated from the model.

The distribution of the models will be assessed and the assumptions of the models will be checked. If any of the assumptions are violated the first option would be to apply a suitable transformation to the data, if this is not possible then a non-parametric test will be applied to the data (i.e. chi-Squared test). If a non-parametric test is adopted, it will not be possible to adjust for covariates.

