2.1.1 PRIMARY OUTCOME FOR THE PRIMARY OBJECTIVE

The primary outcome is 'living at home' at 6 months.

Living at home is defined as the inverse of death or living in a residential care setting. It is derived from a place of assessment variable, (a 5-category variable, 1 = hospital assessment centre, 2 = in-patient hospital, 3 =

residential care home, 4 = patient's home, and 5 = other) and the patient's death status (0 = alive, 1 = dead) reported at the 6 months visit. Living at home will be coded as a binary variable (1 = alive and living at home, 0 = otherwise (including deaths and living at residential care). Living at home will be computed as 0 if death status = 1 (dead) or place of assessment = 3 (residential care home), or place of assessment = 5 (other) and other = "Nursing Home" (variable *assessoth6m*), otherwise living at home = 1, as long as patient also has a visit date for the particular time point.

Additional information about the residential care (variable *admitryr*) will be used for patients with a place of assessment = 1 (hospital assessment centre) or = 2 (in-patient hospital) to verify where these patients were admitted from. If patients have been in residential care they will be coded as 'not living at home', if patients are not recorded as having been in residential care then they will be assumed to have been admitted from 'home'.

If the patient's death status is missing and the patient's place of assessment has been completed, the patient will be assumed to be alive. In cases where the place of assessment and death status are conflicting (i.e. place of assessment is complete but the patient has been reported as dead) then the patient death form CRF will be used to confirm whether the patient is alive or dead. If the place of assessment and the patient's death status are both missing, then the primary outcome will be missing. This information will be coded as a binary variable (0 = death or not living at home, 1 = alive and living at home) to be used in the analysis.

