2.1.2 SECONDARY OUTCOMES FOR THE PRIMARY OBJECTIVE

The secondary outcomes for the primary objective are: presence of delirium, mortality, new long-term residential care, cognitive impairment, activities of daily living, quality of life, quality adjusted survival, length of stay in hospital, readmission or transfer to hospital, resource use (health and social care and informal care), and costs and cost-effectiveness, see Appendix III for questionnaire scoring.

1) Incident and Persistent of Delirium (CAM) at baseline, 3 days, 5 days, and 1 month

The Confusion Assessment Method (CAM) diagnostic algorithm [1] is used to derive a variable for delirium, and is assessed at baseline, 3 days, 5 days and 1 month follow-up. CAM is split into 4 features (acute onset and fluctuating course, inattention, disorganized thinking, and altered level of consciousness).

Feature 1 (acute onset and fluctuating course) is present if there is evidence of an acute change in mental status from the patient's baseline (variable *cam1*) **AND** the behaviour fluctuated during the interview (variable *cam2b*). Feature 2 (inattention) is present if the patient had difficulty focusing attention during the interview in either mild or marked form (variable *cam2a*). Feature 3 (disorganized thinking) is present if the patient's thinking is disorganised or incoherent (variable *cam3*). Feature 4 (altered level of consciousness) is present if the patient's level of consciousness is anything other than alert (or uncertain) (variable *cam4*).

A diagnosis of delirium will be coded as a binary variable (0 = absent, 1 = present) and is present if the patient is positive for a presence of acute onset and fluctuating discourse (feature 1) **AND** positive for inattention (feature 2) **AND EITHER** disorganised thinking (feature 3) **OR** altered level of consciousness (feature 4).

If 'not applicable' is answered it shall be treated as 'no', and delirium will be calculated for each patient unless all the items from these sections are missing, in this case the delirium score will be coded as missing.

2) Mortality at 3 days, 5 days, 1 month, 6 months and 12 months

Patient mortality status is collected at 3 days, 5 days, 1 month, 6 months and 12 months after randomisation on the respective follow-up CRFs, date and details of a patient's death is collected on

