the patient death form CRF. If a patient has been reported as dead at 6 or 12 months on the follow-up CRF (variable *deathyn*) it will be checked against the date of death on the Patient Death CRF (variable *deathdat*). If there is conflicting information between the follow-up form and the death form, the death form will overrule the Follow up CRF. If neither the follow-up form nor the death form have been completed then the TM will check with the site if the patient has died.

3) New long-term residential care at 1 month and 6 months

Subsequent admission to residential care is measured at 1 month, and 6 months follow up (variable *admitryn*). This will be coded as a binary variable (0 = No, 1 = Yes). The 6 months admission to residential care data will include the data collected at the 1 month time point.

4) Cognitive impairment at baseline and 6 months (MoCA)

The Montreal Cognitive Assessment (MoCA) [2] is used to derive a variable for cognitive impairment, and is assessed at baseline and 6 months follow-up. The MoCA comprises 8 sections with a total of 30 questions administered by a qualified health professional (variables *mocavis mocanam mocaatt mocalan mocaabs mocarec mocaori*). A total MoCA score will be derived by summing the score from each section of the questionnaire, only patients with complete MoCA will have a total MoCA score computed, an extra point is added to the total score if the patient has 12 or less years of education. The possible range of scores for the MoCA range from 0 to 30, with a score of 26 or above is considered normal. If the patient is visually impaired or if they are frail and unable to write and draw, the visuospatial/executive section (variable *mocavis*) and the naming section (variable *mocanam*) are excluded and is scored out of 22 instead, a score of 18 or above is considered normal. Cognitive impairment will be coded as a binary variable (0 = score less than 26 (less than 18 if visually impaired), 1 = score 26 or more (18 or more if visually impaired)).

5) Activities of daily living at baseline and 6 months (Barthel index)

The Barthel index [3] is used to derive a variable for activities of daily living, and is assessed at baseline and 6 months follow-up. The Barthel index consists of 10 questions (variables *biadl1 – biadl10*), and has a possible range of scores from 0 (completely dependent) to 20 (completely independent). The final Barthel index score is derived by summing the 10 items.

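### In two secondary outcomes, mortality and cognitive impairment, the value 1 is written as the opposite of the named event; separately, and less certainly, the CAM rule scores some undetermined cases as no delirium

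*SAP*

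**What the plan says.** **Mortality.** Section 5.1(3) describes the follow-up variable *deathyn* "and is a binary variable (0 = dead, 1 = alive" and then states: "The adjusted relative risk and 95% CI and p-value for mortality at each time point will be estimated from the model". Section 2.1.1 has the reverse coding, "death status (0 = alive, 1 = dead", and relies on it in the primary-outcome derivation: "Living at home will be computed as 0 if death status = 1 (dead". Section 2.1.2(2) names *deathyn* as the follow-up CRF item on which death is reported, so the two sections appear to describe the same information.

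**Cognition.** Section 2.1.2(4) states: "Cognitive impairment will be coded as a binary variable (0 = score less than 26 (less than 18 if visually impaired), 1 = score 26 or more". Of the full MoCA, the same paragraph says "with a score of 26 or above is considered normal". Section 5.1(5) refers back to this binary variable and promises an adjusted relative risk for cognitive impairment at 6 months.

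**Delirium.** In section 2.1.2(1), delirium requires feature 1 and feature 2, plus feature 3 or feature 4. An answer of not applicable counts as no. On missing items the rule is "delirium will be calculated for each patient unless all the items from these sections are missing". There is no separate rule for a single blank item.

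**Model.** Section 11 replaces the protocol's mixed logistic regression with a generalised linear mixed model so that relative risks can be obtained. Neither section 4.1 nor section 11 names a link function.

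**The concern.** A model for a 0/1 outcome normally takes 1 as the event. Under the written codes, a table row labelled mortality could then hold a relative risk of survival, and a row labelled cognitive impairment a relative risk of normal cognition. A benefit would look like harm.

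The move away from logistic regression makes this worse. Swapping the event simply inverts an odds ratio, so a reader who spots the reversal can recover the intended figure. A relative risk cannot be recovered that way.

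The plan's checks may not catch the error. The minimum validation in section 10 covers the primary, sensitivity and safety analyses and later the 12-month living-at-home outcome. Secondary mortality and cognition are not in it.

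The CAM question is of a different kind. Here the event is coded correctly (1 = present), but a diagnosis is assigned even when the answers given do not determine it.

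**Working it through.** **Inputs.** The plan gives no expected rates for mortality, MoCA or CAM. Its only planning rates, in section 2.3, are 50% vs 40% with a relative risk of 0.8, and these reproduce: 0.40/0.50 = 0.80. All other rates below are illustrative assumptions.

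**1. Effect of swapping the event.** With event risk p1 in the hospital-at-home arm and p0 in the inpatient arm:

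- relative risk of the event = p1/p0
- relative risk of the complement = (1 − p1)/(1 − p0)

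| Case | p1 vs p0 | RR, named event | RR, complement | Reciprocal of the named-event RR |
|---|---|---|---|---|
| Section 2.3 rates | 40% vs 50% | 0.80 | 0.60/0.50 = 1.20 | 1.25 |
| Death (assumed) | 16% vs 20% | 0.80 | 0.84/0.80 = 1.05 | 1.25 |
| Impairment (assumed) | 85% vs 90% | 0.94 | 0.15/0.10 = 1.50 | 1.06 |

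With a true relative risk of death of 0.80 and inpatient mortality from 10% to 30%, the survival relative risk runs from 0.92/0.90 = 1.02 to 0.76/0.70 = 1.09.

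**2. Precision in the mortality example.** 1050 × 0.94 = 987 evaluable patients, split 658 and 329. The standard error of the log relative risk is √[(1 − p0)/(329·p0) + (1 − p1)/(658·p1)]. Unadjusted, this gives:

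- death: 0.80 (95% CI 0.61 to 1.06), z = −1.57
- survival: 1.05 (95% CI 0.99 to 1.12), z = 1.51

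The strength of evidence hardly changes. What changes is the direction and size of the reported effect.

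**3. Partly missing CAM.** Five items feed the algorithm (*cam1*, *cam2b*, *cam2a*, *cam3*, *cam4*). With each recorded as positive, negative or blank there are 3⁵ = 243 patterns. Removing the 2⁵ = 32 complete patterns and the one fully blank pattern leaves 210. If a blank is read as not positive:

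- 2 are still delirium present (features 1 and 2 positive, one of features 3 and 4 positive, the other blank)
- 150 are negative whatever the blanks would have been
- 58 are scored absent although the blanks could have made them positive

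These are counts of patterns, not of patients.

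**4. Effect on the delirium relative risk.** Let q1 and q0 be the shares of truly delirious patients who lose a decisive item in the hospital-at-home and inpatient arms, with no false positives. The observed relative risk is p1(1 − q1)/[p0(1 − q0)]. Assume true delirium of 20% vs 25%, a relative risk of 0.80:

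- q1 = 20%, q0 = 10%: 0.160/0.225 = 0.71
- q1 = 10%, q0 = 20%: 0.180/0.200 = 0.90
- q1 = q0: 0.80, unchanged, with lower rates in both arms

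**The case against.** The intended event is not in doubt, because section 5.1 names mortality and cognitive impairment as the targets. The mortality coding looks like a slip in one parenthesis: the parallel items *admitryn* and *hadmityn* use 1 = Yes, and section 2.1.1 uses 1 = dead. If the data follow section 2.1.1, the model returns the relative risk of death as intended. Deaths are also to be summarised at each time point, so a reversed estimate would be visible beside them. This stands for mortality and makes that harm conditional. It is weaker for cognition, where the binary variable is created by the SAP's own rule and no other coding is given. Nor does noticing the reversal repair the estimate: inverting 1.05 gives 0.95, not 0.80.

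On the CAM, the express rule for scoring no covers answers of not applicable. Scoring a blank as negative is only implied. The items, as described, rate what is seen of the patient, and nothing in the plan says that sicker patients leave blanks or that the arms would differ. This also stands, and it is why the CAM point carries less weight.

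A reader might infer more than the document supports:

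- **That the primary outcome is miscoded.** Section 2.1.1 is consistent in itself. Trouble would arise only if its rule were applied to data coded as in section 5.1, and nothing shows that.
- **That the subgroup result in section 7 is wrong.** Calling impaired patients MoCA positive clashes with the coding, but relabelling a two-level factor changes neither the interaction p-value nor the effect within each level.
- **That the fault depends on a log link.** No link is named; the point holds for any model that returns relative risks.

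**Conclusion.** The coding fault holds. The two mortality codings contradict each other, and the cognitive impairment variable has 1 for the absence of impairment. If 1 is modelled as the event, the cognition estimate is for the complement of the named event; the mortality estimate is too, on the further condition that the data follow section 5.1. The illustrative shifts, 0.80 to 1.05 and 0.94 to 1.50, depend on assumed rates. That the result is not the reciprocal does not depend on them.

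The CAM fault is separate and less certain. It concerns patients whose answered items leave the diagnosis open, and it rests on reading a blank as negative. It lowers the delirium rates. It biases the relative risk if the loss differs by arm, to 0.71 or 0.90 from 0.80 in the examples, and leaves it unchanged with equal loss and no false positives. It would be too strong to say that three relative risks are wrong, or that every incomplete CAM is scored negative.

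All the outcomes concerned are secondary. The coding should be corrected before analysis because the repair is nearly free; the CAM rule is a worthwhile clarification alongside it.

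**What to change.** 1. In section 5.1(3), code mortality 1 = dead, 0 = alive, to agree with section 2.1.1, and confirm that the *deathyn* data are coded that way.
2. In section 2.1.2(4), code cognitive impairment 1 = below the cut-off (26, or 18 on the 22-point version) and 0 = at or above it.
3. For each binary outcome in section 5.1, name the event being modelled.
4. In section 2.1.2(1), code delirium present or absent only when the answered items determine the algorithm (for example, absent if feature 1 or feature 2 is answered as not present). Otherwise set it to missing. State the handling of blanks separately from that of not-applicable answers.

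Items 1 to 3 cost a few words and some derivation code. Item 4 costs the same, plus slightly more missing CAM values.

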2.2 TARGET POPULATION

Inclusion Criteria

- Participant is willing and able to give informed consent for the participation in the study.
- If the participant lacks capacity to consent they have a relative or friend who is a 'personal consultee' or Independent Mental Capacity Advocate who will be invited to advise on whether they believe that participation in the study would be in accordance with the values and interests of the individual.
- Male or Female, aged ≥ 65 years.
- Patient had been referred to the admission avoidance HAH service with CGA and would otherwise require hospital admission for an acute medical event. This will include patients presenting with delirium, functional decline, dependence, falls, immobility or a background of dementia presenting with physical disease.
- In the Investigator's opinion, is able and willing to comply with all trial requirements.
- Willing to allow his or her General Practitioner and consultant, if appropriate, to be notified of participation in the trial.
- English speaking.

The presence of a carer will not be a requirement for enrolment and will depend on the individual circumstances of the patient; this will be at the discretion of the clinician responsible for the patient, as is current clinical practice in each centre.

Exclusion Criteria

- Patients with acute coronary syndrome, this includes myocardial infarction and unstable angina and is characterised by cardiac chest pain and is associated with ECG changes.
- Patients presenting with symptoms which require an acute surgical assessment.
- Patients with a suspected stroke.
- Patients who are receiving end of life care as part of a palliative care pathway.
- Patients who refuse HAH service.
- Patients considered by the clinical staff to be too high risk for home based care, for example those who are physiologically unstable, who are at risk to themselves or if the carer reports HAH care who not be acceptable (in keeping with existing clinical practices for HAH).
- Patients living in a residential setting.

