2.3 SAMPLE SIZE

The sample size is calculated for the primary outcome: living at home at 6 months follow up (the inverse of death or living in a residential care setting), for a 2:1 randomisation ratio with 2/3rd randomized to admission avoidance HAH with CGA and 1/3 to inpatient CGA. Several sources informed our estimate of effect size; these were one of the trials included in the IPD meta-analysis of HAH which recruited frail older people who required hospital level care (similar to the study population we plan to recruit), an audit of 750 patients who received HAH + CGA in Lanarkshire, the RCTs of CGA included in the Cochrane Review and the pooled estimate for the relative effect at 6 months obtained from the IPD Cochrane Review of HAH (3 trials, 607 participants) which was an adjusted Hazard Risk of 0.62 (95% CI 0.45 to 0.87) for mortality. Our proposed study effect estimate is based on a control group (CGA hospital) event rate at 12 months of 50% with a 10% reduction in living in a residential setting to 40% in the CGA at home group, equal to a relative risk of 0.8 which lies towards the top end of the 95% CI for the pooled estimate. We have calculated that a sample size of 1050 to achieve around 83% power at a significance level of 0.05 to detect a 10% absolute difference, assuming a control group event rate at 12 months of 50% and 6% attrition.

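### The 6-month MoCA is compared between arms only as above or below a cut of 26 (18 on the 22-point form); analysing the score would recover precision, by an amount that the SAP's figures cannot fix

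*SAP*

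**What the plan says.** - **Scoring (SAP 2.1.2, item 4).** MoCA section scores are summed to a total of 0 to 30, computed only when the test is complete. Patients who are visually impaired, or too frail to write and draw, skip the visuospatial/executive and naming sections and are scored out of 22. Then "Cognitive impairment will be coded as a binary variable", cut at 26, or at 18 on the shorter form.
- **Analysis (SAP 5.1, item 5).** "This is converted into a binary variable (see section 2.1.2"). A generalised linear mixed model gives an adjusted relative risk, with the baseline MoCA entered as a score.
- **Nearest comparator (SAP 5.1, item 6).** "Activities of daily living is measured at baseline and 6 months by the Barthel index and is a continuous variable". It gets a linear mixed model.
- **Population (SAP 2.2).** On eligible presentations: "This will include patients presenting with delirium, functional decline, dependence, falls, immobility or a background of dementia presenting with physical disease".
- **Other cognitive measures.** IQCODE is taken at baseline only. CAM delirium is compared at 3 days, 5 days and 1 month (5.1, item 2).
- **Back-up.** Section 6 limits sensitivity analyses to the primary outcome unless stated otherwise, and states none for MoCA.

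**The concern.** The plan keeps the MoCA scale for the covariate and discards it for the outcome. A patient who falls from 20 to 14, or rises from 12 to 18, counts as unchanged. The cut marks the boundary of a normal result, and the patients are frail older people, some with delirium at entry or a background of dementia. The cut therefore probably lies well above the middle of the distribution, where it is least informative. No other planned analysis uses the 6-month score. What is at stake is the precision of the one 6-month comparison of cognitive function: a modest difference between care settings, in either direction, is harder to detect than the collected data allow.

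**Working it through.** **1. The plan's own power figure.** Section 2.3 gives "a sample size of 1050 to achieve around 83% power" "at a significance level of 0.05 to detect a 10% absolute difference", with event rates of 50% and 40%, 2:1 allocation and 6% attrition.

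- Evaluable: 1050 × 0.94 = 987, so 329 inpatient and 658 hospital at home.
- Pooled proportion: (329 × 0.5 + 658 × 0.4)/987 = 0.4333. Null SE = √(0.4333 × 0.5667 × (1/329 + 1/658)) = 0.03346. Alternative SE = √(0.25/329 + 0.24/658) = 0.03354.
- Power = Φ((0.1 − 1.96 × 0.03346)/0.03354) = 84.8%. With the continuity correction it is 83.1%.

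The stated figure reproduces at two-sided 5%. It concerns the primary outcome only. For MoCA the SAP gives no mean, SD, effect or expected number, so everything below rests on assumptions and is shown as a range.

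**2. Information kept by a cut.** For a normal score with share q below the cut, efficiency relative to the full score is E = φ(z)²/(q(1 − q)), where z is the cut in SD units. The maximum, at the median, is 2/π = 0.637. Taking the cut at 25.5, mean 20 and SD 5.5 give z = 1.0, q = 0.841 and E = 0.2420²/(0.841 × 0.159) = 0.44. Over SD 5 to 6, E is 0.27–0.35 at mean 18, 0.40–0.47 at mean 20, 0.53–0.56 at mean 22 and 0.62 at mean 24.

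**3. What that does to power.** If the full-scale analysis has power Φ(λ − 1.96), the cut has power Φ(λ√E − 1.96).

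| Share below 26 | E | Cut, if full scale has 80% | Cut, if full scale has 90% |
|---|---|---|---|
| 50% | 0.64 | 61% | 73% |
| 60% | 0.62 | 60% | 73% |
| 70% | 0.58 | 57% | 69% |
| 80% | 0.49 | 50% | 62% |
| 90% | 0.34 | 37% | 48% |
| 95% | 0.22 | 26% | 34% |

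**4. Simulation with baseline adjustment.** Scores were rounded and held to 0–30. A linear model on the score was compared with a logistic model on 26 or more, both adjusted for arm and baseline score. Centre, gender, IQCODE and the 22-point form were left out. SD 5.5, correlation 0.6, 2:1 allocation, true difference 1 point:

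| Mean | 400 vs 200: full / cut | Loss | 520 vs 260: full / cut | Loss |
|---|---|---|---|---|
| 18 | 78% / 25% | 53 | 84% / 32% | 52 |
| 20 | 73% / 35% | 38 | 81% / 41% | 40 |
| 22 | 71% / 40% | 31 | 84% / 53% | 31 |
| 24 | 70% / 47% | 23 | 80% / 51% | 29 |

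Each cell is 500 simulated trials, so a power has a standard error of up to √(0.25/500) = 2.2 points.

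**5. A smaller effect or fewer patients.** With a 0.5-point difference (same SD and correlation, means 18 to 24):

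- 400 vs 200: 24–30% full scale against 10–15% cut; repeat runs put the loss at about 8 to 20 points.
- 267 vs 133: 18–20% against 6–12%; loss about 5 to 12 points.

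Fewer patients alone do not shrink the loss this far. With 400 patients in all, a 1-point difference, SD 5 and correlation 0.5, power goes from 54% to 34% with 60% below the cut (20 points) and from 58% to 13% with 95% below (45 points).

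**The case against.** **The size is not in the document.** This stands. The larger losses need a difference of about 1 point. At 0.5 points both analyses are weak, and the loss in points is much smaller.

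**The share below 26 is inferred.** The entry criteria also include falls and immobility, delirium at presentation precedes this outcome by six months, and only survivors who complete the test are scored. This weakens the case for the lowest means. It does not rescue the cut, since even a cut at the median keeps only about 64%.

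**A reader might infer that cognition is otherwise uncompared.** The SAP does not support that: CAM, which covers inattention and disorganised thinking, is compared up to 1 month. The claim holds for cognitive function at 6 months only.

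**A reader might also infer that a real effect would be reported as no difference.** That is a guess about the write-up. A relative risk with its 95% confidence interval is planned, so imprecision will be visible.

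**The cut is pre-specified, and the outcome is named as a status.** True, and it is not data-driven; a rationale may stand in the protocol, which was not available for this check. But Appendix III lists the same measure as a 0–30 score where higher is better, and section 11 explains why relative risks are wanted for binary outcomes, not why MoCA should be one.

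**The cut puts both forms on one footing.** This is the strongest point in its favour. Percent of maximum would not do so (26/30 = 86.7%, 18/22 = 81.8%), and adjusting for the form used at 6 months would condition on frailty seen after randomisation, which treatment may affect. It rules out those two repairs, not a score analysis as such.

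**Conclusion.** The point holds as a matter of precision on a secondary outcome. If the score is roughly normal, the planned analysis keeps at most about 64% of the information, and about 27 to 62% for assumed means of 18 to 24. The cost in power is about 20 to 50 points if the full-scale comparison would have about 70 to 90% power, and about 5 to 20 points if the true difference is 0.5 points. No single figure can be given, because the SAP supplies none of the inputs. The direction does not depend on them. The simulations contain no patients on the 22-point form, so the exact gain from the common-section score proposed below is untested. The primary outcome and its stated power are unaffected. The change is worth making because it is cheap, not because the present analysis is invalid.

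**What to change.** **In SAP 5.1 item 5,** make the main analysis a linear mixed model on the 6-month MoCA score, with arm, baseline MoCA score, gender and IQCODE as fixed effects and centre as a random effect. Report the adjusted mean difference with its 95% confidence interval. Keep the 26/18 relative risk beside it, and state which category is the event, since 2.1.2 item 4 codes 1 for scores at or above the cut.

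**In SAP 2.1.2 item 4,** define a score that every patient has whichever form was used, for example the total of the sections common to both forms (30 − 8 = 22 points), taken at both visits. This needs no adjustment for the form used after randomisation. State whether it carries the education point. Add the 30-point total among full-form completers as a supportive analysis; that set is selected after randomisation, so it should not be the main one.

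**Cost.** Revised wording and one model of the kind already specified for the Barthel index, on section scores already collected. It should be settled before the 6-month data are analysed. There are two small downsides: a mean difference is less immediate to clinicians than a proportion impaired, and the common-section score omits the visuospatial and naming items.
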